8.2.2. Laboratory Assessments

All protocol required laboratory assessments, as defined in the SoA (see Section 1.3), must be performed by the central laboratory. Laboratory assessments must be conducted in accordance with the Central Laboratory Manual and Protocol SoA. Laboratory requisition forms must be completed, and samples must be clearly labeled with the participant number, protocol number, site/center number, and visit date. Details for the preparation and shipment of samples will be provided by the central laboratory. Reference ranges for all safety parameters will be provided to the site by the central laboratory.

- The investigator must review the laboratory report, document this review, and record any clinically relevant changes occurring during the study in the AE Section of the CRF. The laboratory reports must be filed with the source documents. Clinically significant abnormal laboratory findings are those which are not associated with the underlying disease, unless judged by the investigator to be more severe than expected for the participant's condition.
- All laboratory tests with values considered clinically significantly abnormal during participation in the study should be repeated until the values return to normal or baseline or are no longer considered significantly abnormal by the investigator or medical monitor.
- If such values do not return to normal/baseline within a period of time judged reasonable by the investigator, the etiology should be identified and the sponsor notified.
- All protocol-required laboratory assessments must be conducted in accordance with the laboratory manual and the protocol Time and Events table.

If additional non-protocol specified laboratory assessments are performed at the institution's local laboratory and result in a change in participant management or are considered clinically significant by the investigator (e.g., SAE or AE or dose modification) the results must be recorded in the eCRF. Local laboratory services may be used to verify pending laboratory parameters only after consultation and agreement with the study team.

Refer to the lab manual for appropriate processing and handling of samples to avoid duplicate and/or additional blood draws.

Labs will be automatically graded by the central lab according to the DAIDS toxicity scales (See Section 10.4 "Division of AIDS Table for Grading the Severity of Adult and Pediatric Adverse Events").

For fasting laboratory assessments, an overnight fast is preferred; however, a minimum of a 6 hour fast is acceptable.

Table 4 includes lab parameters to be assessed as per the SoA (see Section 1.3). In addition to the protocol-specified laboratory assessments the study Medical Monitor, in

collaboration with the site investigator, may request additional central laboratory assessments be performed to support safety profiling and case management of individual study participants.

Table 4 Safety Laboratory Assessments

Hematology			
Platelet count		Automated WBC differential:	
RBC count		Neutrophils	
WBC count (absolute)		Lymphocytes	
Hemoglobin		Monocytes	
Hematocrit		Eosinophils	
MCV		Basophils	
Clinical Chemistry			
BUN	Potassium	AST	Total bilirubin ^a
Creatinine	Chloride	ALT	Albumin
Glucose ^c	Total CO ₂	Alkaline phosphatase	Creatine phosphokinase
Sodium	Lipase	Phosphate	Creatinine clearance ^b
Fasting Lipid Panel^d			
Total cholesterol			
HDL cholesterol			
LDL cholesterol			
Triglycerides			
Other Tests			
Plasma HIV-1 RNA ^e			
CD4+ and CD8+ cell counts [CD4/CD8 ratio] ^f			
Peripheral Blood Mononuclear Cells (PBMCs): Day 1, Month 12, Withdrawal only			
Hepatitis B (HBsAg), anti-HBc, anti-HBsAg, and hepatitis C antibody (Screening) ^g			
Syphilis serology + Reflex Rapid Plasma Reagin (RPR) (Screening and Baseline)			
Prothrombin Time (PT)/International Normalized Ratio (INR)/ Partial Thromboplastin Time (PTT)			
Pregnancy test for women of childbearing potential ^h			
Urinalysis, urine albumin/creatinine ratio, and urine protein/creatinine ratio, urine phosphate			
Genetics Sample			
Follicle stimulating hormone (FSH) and estradiol (only for instances when postmenopausal status is questionable)			
Renal biomarkers including Cystatin-C (blood), Retinol Binding Protein (RBP, blood/urine); and Beta-2-Microglobulin (B2M, blood/urine) ⁱ			
Bone biomarkers including: Bone-specific alkaline phosphatase, procollagen type 1 N-propeptide, type 1 collagen cross-linked C-telopeptide, osteocalcin, 25 hydroxy-Vitamin D ^j			
CCI			
HbA1c, Insulin, HOMA-IR			

MCV = mean corpuscular volume, RBC = red blood cells, WBC = white blood cells, BUN = Blood urea nitrogen, AST=aspartate aminotransferase, ALT = alanine aminotransferase, CO₂ = carbon dioxide, HDL = high density lipoprotein, LDL = low density lipoprotein, HBsAg= hepatitis B virus surface antigen, PT/INR = prothrombin time/international normalized ratio.

- Direct bilirubin will be reflexively performed for all total bilirubin values $>1.5 \times$ ULN.
- Glomerular filtration rate (GFR) will be estimated by the central laboratory using the Chronic Kidney Disease Epidemiology Collaboration (CKD-EPI) [Levey, 2009].
- For fasting glucose assessments, an overnight fast is preferred; however, a minimum of a 6-hour fast is acceptable for participants with afternoon appointments.
- For fasting lipids assessments, an overnight fast is preferred; however, a minimum of a 6-hour fast is acceptable for participants with afternoon appointments.
- For participants meeting virologic withdrawal criteria, plasma samples will be analyzed in attempt to obtain genotype/phenotype data.
- CD8+ cells will only be reported at Baseline, Day 1, Months 1, 6, and 12.

- g) HBV DNA will only be performed for participants with a positive anti-HBc and negative HBsAg and negative anti-HBs (past and/or current evidence).
- h) Urine pregnancy test/ serum pregnancy test will be performed according to the SoA (Section 1.3).
- i) The intention is to utilize these biomarker data for research purposes; the sponsor will not be reporting real-time results of these assessments to the investigator, except for Cystatin C (Day 1 only) and 25 hydroxy-Vitamin D.

Planned time points for all safety assessments are provided in the SoA (Section 1.3).

8.2.3. Physical Examinations

Physical exams should be conducted as part of normal routine clinical care. Abnormalities noted during any exam must be recorded in the eCRF (e.g., in the current medical conditions or AE logs).

- A complete physical examination will include, at a minimum, assessment of the Cardiovascular, Respiratory, Gastrointestinal, and Neurological systems. Height and weight will also be measured and recorded as per the SoA in Section 1.3 above.
- A brief physical examination will include, at a minimum, assessments of the skin, lungs, cardiovascular system, and abdomen (liver and spleen).
- The site of IM injection administration should be assessed at every visit for signs of any possible reaction. See Section 8.3.11.6 for additional information.
- Investigators should pay special attention to clinical signs related to previous serious illnesses.

8.2.4. Vital Signs

Vital signs will be measured in semi-supine position after 5 minutes rest and will include temperature, systolic and diastolic blood pressure and pulse rate. These will be recorded as per the SoA, in Section 1.3.

8.2.5. Electrocardiograms

A 12-lead ECG will be performed in a semi-supine position. On Day 1, (Baseline), ECGs should be performed in triplicate prior to first dose. At Day 1, Month 1 (OLI) and Month 12 (OLI)/Month 11 (D2I) of the Maintenance Phase, a 2-hour post dose ECG will be performed for participants receiving CAB LA + RPV LA with an allowable window of ± 30 minutes. An ECG machine that automatically calculates the heart rate and measures PR, QRS, QT, and QTc intervals is preferred, and these calculated numbers can be used for reporting purposes. Otherwise, an appropriately qualified ECG reader must interpret the results. The same interpreter should assess all ECGs for each participant. Regardless, each ECG should be reviewed by a qualified ECG reader. The qualified ECG reader will make the non-calculated ECG interpretations. Refer to the SoA for collection timepoints (Section 1.3). Refer to Section 7.1.4 for [QTc] withdrawal criteria and additional [QTc] readings that may be necessary.

8.2.6. Suicidal Ideation and Behaviour Risk Monitoring

Participants with HIV infection may occasionally present with symptoms of depression and/or suicidal ideation or behavior. In addition, there have been some reports of depression, suicidal ideation and behavior (particularly in participants with a pre-existing history of depression or psychiatric illness) in some patients being treated with INIs. Additionally, depression and anxiety has been reported in some participants being treated with RPV. Therefore, it is appropriate to monitor and closely observe participants prospectively before and during treatment for suicidal ideation and/or behavior, or any other unusual changes in behavior. It is recommended that the Investigator consider mental health consultation or referral for participants who experience signs of suicidal ideation or behavior.

Participants presenting with new onset/treatment emergent depression should be advised to contact the investigator immediately if symptoms of severe acute depression (including suicidal ideation/attempts) develop, because medical intervention and discontinuation of the study medication may be required.

Assessment of treatment-emergent suicidality will be monitored during this study using the electronic version of the Columbia Suicide-Severity Rating Scale (eC-SSRS). The definitions of behavioural suicidal events used in this scale are based on those used in the Columbia Suicide History Form [Posner, 2007]. Questions are asked on suicidal behavior, suicidal ideation, and intensity of ideation. Screening visit questions will be in relation to lifetime experiences and current experiences (within the past 2 months) and all subsequent questioning in relation to the last assessment. The eC-SSRS is to be administered as a patient completed questionnaire specified in the SoA (Section 1.3). The eC-SSRS will be conducted electronically by telephone or by computer/tablet connected to the internet.

Additionally, the investigator will collect information using the Possible Suicidality-Related AE (PSRAE) eCRF form in addition to the Adverse Event (non-serious or Serious Adverse Events) eCRF form on any participant that experiences a possible suicidality-related adverse event while participating in this study. This may include, but is not limited to, an event that involves suicidal ideation, a preparatory act toward imminent suicidal behavior, a suicide attempt, or a completed suicide. The investigator will exercise his or her medical and scientific judgment in deciding whether an event is possibly suicide related. PSRAE forms should be completed and reported to ViiV/GSK within one week of the investigator diagnosing a possible suicidality-related adverse event. All sites should have a plan in place for managing possible risks for suicide related events.

8.3. Adverse Events and Serious Adverse Events

The definitions of an AE or SAE can be found in Section 10.2.

AEs will be reported by the participant (or, when appropriate, by a caregiver, surrogate, or the participant's legally authorized representative).

The investigator and any qualified designees are responsible for detecting, documenting, and reporting events that meet the definition of an AE or SAE and remain responsible for following up AEs that are serious, considered related to the study intervention or the study, or that caused the participant to discontinue the study intervention and/or study (see Section 7).

Please refer to [Appendix 11](#) in Section 10.11 for study management information during the COVID-19 pandemic.

8.3.1. Time Period and Frequency for Collecting AE and SAE Information

[figure not shown]
- Any SAEs assessed as related to study participation (e.g., protocol-mandated procedures, invasive tests, or change in existing therapy) or related to a GSK product will be recorded from the time a participant consents to participate in the study up to and including any follow-up contact.
- All SAEs will be recorded and reported to the sponsor or designee immediately and under no circumstance should this exceed 24 hours. The investigator will submit any updated SAE data to the sponsor within 24 hours of it being available.
- AEs will be collected from the start of Study Treatment until the final follow-up contact, at the timepoints specified in the SoA (Section 1.3).
- Medical occurrences that begin prior to the start of study treatment but after obtaining informed consent may be recorded on the Medical History/Current Medical Conditions Section of the eCRF.
- The method of recording, evaluating and assessing causality of AEs and SAEs plus procedures for completing and transmitting SAE reports to GSK are provided in Section 10.2.
- Investigators are not obligated to actively seek AEs or SAEs in former study participants. However, if the investigator learns of any SAE, including a death, at any time after a participant has been discharged from the study, and he/she considers the event reasonably related to the study treatment or study participation, the investigator must promptly notify GSK.

8.3.2. Method of Detecting AEs and SAEs

The method of recording, evaluating, and assessing causality of AEs and SAEs and the procedures for completing and transmitting SAE reports are provided in [Appendix 3](#).

Care will be taken not to introduce bias when detecting AE and/or SAE. Open-ended and non-leading verbal questioning of the participant is the preferred method to inquire about AE occurrence. Appropriate questions include:

CCI - This section contained Clinical Outcome Assessment data collection questionnaires or indices, which are protected by third party copyright laws and therefore have been excluded.

8.3.3. Follow-up of AEs and SAEs

After the initial AE/SAE report, the investigator is required to proactively follow each participant at subsequent visits/contacts. All SAEs, and non-serious AEs of special interest will be followed until the event is resolved, stabilized, otherwise explained, or the participant is lost to follow-up (as defined in Section 7.2). Further information on follow-up procedures is given in Section 10.2.

8.3.4. Prompt Reporting of Serious Adverse Events and Other Events

SAEs, pregnancies, and liver function abnormalities meeting pre-defined criteria will be reported promptly by the investigator to the medical monitor once the investigator determines that the event meets the protocol definition for that event. Any seizure or suspected seizure should be reported in an expedited manner, as noted in Table 5.

Criteria for liver chemistry stopping and follow-up criteria are in Section 7.1.1.

Table 5 Reporting of Serious Adverse Events and Other Events

Type of Event	Initial Reports		Follow-up Information on a Previous Report	
	Time Frame	Documents	Time Frame	Documents
All SAEs	24 hours	“SAE” data collection tool	24 hours	Updated “SAE” data collection tool
Cardiovascular or death event	Initial and follow-up reports to be completed when the cardiovascular event or death is reported ^a	“CV events” and/or “death” data collection tool(s) if applicable	Initial and follow-up reports to be completed when the cardiovascular event or death is reported ^a	Updated “CV events” and/or “death” data collection tool(s) if applicable
Pregnancy	24 hours	“Pregnancy Notification Form”	Within 24 hours of investigator awareness of pregnancy outcome	“Pregnancy Follow-up Form” and SAE if required
Seizure or suspected seizure	24 hours	eCRF	24 hours	eCRF
Suspected ABC HSR in participants receiving Oral SOC during the Long-Term Follow-Up Phase ^b	1 week	ABC HSR eCRF	1 week	Updated ABC HSR eCRF
ALT $\geq 3 \times$ ULN and bilirubin $\geq 2 \times$ ULN (>35% direct) (or ALT $\geq 3 \times$ ULN)	24 hours ^c	“SAE” data collection tool. “Liver Event eCRF” and “Liver Imaging” and/or “Liver Biopsy” eCRFs, if applicable ^d	24 hours	Updated “SAE” data collection tool/“Liver Event” documents ^d
ALT $\geq 5 \times$ ULN that persists ≥ 2 weeks	24 hours ^c	Liver Event eCRF ^d	24 hours	Updated Liver Event eCRF ^d
ALT $\geq 8 \times$ ULN	24 hours ^c	Liver Event eCRF ^d	24 hours	Updated Liver Event eCRF ^d
ALT $\geq 3 \times$ ULN (if baseline ALT is <ULN) or ALT ≥ 3 fold increase from baseline value with appearance or worsening of symptoms of hepatitis or hypersensitivity	24 hours ^c	Liver Event eCRF ^d	24 hours	Updated Liver Event eCRF ^d

- Additional details and time frames for reporting supplementary information for cardiovascular and death events are provided in Section 8.3.9.
- ABC HSR eCRF only required if event meets one of the ICH E2A definitions of seriousness.
- GSK must be contacted at onset of liver chemistry elevations to discuss participant safety.
- Liver event documents (i.e., “Liver Event eCRF” and updates, “Liver Imaging eCRF” and/or “Liver Biopsy eCRF”, as applicable) should be completed as soon as possible.

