7.1.1. Liver monitoring event – Increased monitoring

A liver monitoring event is an occurrence of predefined liver chemistry changes that triggers increased monitoring of the participant's liver chemistries, but no action is taken with study treatment unless liver chemistry stopping criteria are met.

Liver monitoring event criteria:

- Baseline ALT $\leq 1.5x$ ULN: ALT $\geq 5x$ ULN and $< 8x$ ULN and bilirubin $< 2x$ ULN without symptoms believed to be related to liver injury or hypersensitivity.
- Baseline ALT $> 1.5x$ ULN: ALT $\geq 3x$ baseline and $< 5x$ baseline and bilirubin $< 2x$ ULN without symptoms believed to be related to liver injury or hypersensitivity

Actions:

- Notify the VH medical monitor within 24 hours of learning of the abnormality to discuss participant safety.
- Participant can continue study intervention
- Participant must return every 2 weeks for repeat liver chemistries (ALT, AST, alkaline phosphatase, bilirubin) until resolution or stabilisation (ALT $< 5 \times$ ULN on 2 consecutive evaluations)
- If at any time participant meets the liver chemistry stopping criteria, proceed as described below

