7.1.2. Liver chemistry stopping criteria

Study treatment or Investigational Product must stop immediately when participant meets one of the criteria described in Table below:

Table 3 Liver Chemistry Stopping Criteria - Liver Stopping Event for phase III - IV studies

Liver Chemistry Stopping Criteria - Liver Stopping Event	
If Baseline ALT ≤ 1.5x ULN	
ALT-absolute	ALT ≥ 8xULN
ALT Increase	ALT ≥ 5xULN but <8xULN persists for ≥2 weeks (with bilirubin <2xULN and no signs or symptoms of acute hepatitis or hypersensitivity)
Bilirubin^{1,2}	ALT ≥ 3xULN and bilirubin ≥ 2xULN (>35% direct bilirubin)
Cannot Monitor	ALT ≥ 5xULN but <8xULN and cannot be monitored every 1 - 2 weeks
Symptomatic³	ALT ≥ 3xULN with symptoms (new or worsening) believed to be related to liver injury or hypersensitivity
If Baseline ALT > 1.5x ULN	
ALT-absolute	ALT ≥ 5x baseline OR > 500 U/L (whichever occurs first)
ALT Increase	ALT ≥ 3x baseline but <5x baseline persists for ≥2 weeks (with bilirubin <2xULN and no signs or symptoms of acute hepatitis or hypersensitivity)
Bilirubin^{1,2}	ALT ≥ 3x baseline OR > 300 U/L (whichever occurs first) and bilirubin ≥ 2xULN
Cannot Monitor	ALT ≥ 3x baseline but <5x baseline and cannot be monitored every 1 - 2 weeks
Symptomatic³	ALT ≥ 3x baseline and symptoms (new or worsening) believed to be related to liver injury or hypersensitivity.

1. Serum bilirubin fractionation should be performed if testing is available. If serum bilirubin fractionation is not immediately available, discontinue study intervention for that participant if ALT ≥3xULN **and** bilirubin ≥2xULN. Additionally, if serum bilirubin fractionation testing is unavailable, **record presence of detectable urinary bilirubin on dipstick**, indicating direct bilirubin elevations and suggesting liver injury.
2. All events of ALT >3xULN and bilirubin >2xULN (>35% direct bilirubin) must be reported as an SAE (excluding studies of hepatic impairment or cirrhosis); INR measurement is not required, and the threshold value stated will not apply to participants receiving anticoagulants.
3. New or worsening symptoms believed to be related to liver injury (such as fatigue, nausea, vomiting, right upper quadrant pain or tenderness, or jaundice) or believed to be related to hypersensitivity (such as fever, rash or eosinophilia).

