9.4.2. Safety and Secondary Analyses

The proportion of participants with plasma HIV-1 RNA <50 c/mL using the Snapshot algorithm is a key outcome at Months 6 and 12 (OLI and BIK)/Months 5 and 11 (D2I) and will be judged against a pre-specified non-inferiority margin of -12%.

Changes from baseline in CD4+ lymphocyte count and in CD4+/CD8+ lymphocyte counts ratio and resistance data will be summarized. The incidence of HIV-1 disease progression (AIDS and death) will be presented.

The proportion of participants with plasma HIV-1 RNA <50 c/mL using the Snapshot algorithm and changes from baseline in CD4+ lymphocyte count will be summarized by subgroups (e.g., age, gender and race)

The observed case dataset will be the primary dataset used for analysis of safety endpoints.

Exposure to study medication, measured by the number of weeks on study drug, will be summarized by treatment group. The proportion of participants reporting AEs will be tabulated for each treatment group. The following summaries of AEs will be provided:

- Incidence and severity of all AEs
- Incidence and severity of treatment related AEs
- Incidence and severity of AEs leading to withdrawal
- Incidence of SAEs

CCI

Laboratory and vital signs data will be summarized by visit and treatment group. In addition, the number and percentage of participants with graded laboratory toxicities (based on DAIDS categories) will be summarized by treatment group. The proportion of participants experiencing changes from Baseline in their National Cholesterol Education Program (NCEP) lipid categories will be summarized by treatment arm. Further details of safety analyses will be included in the RAP.

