- Examples of such events include invasive or malignant cancers, intensive treatment in an emergency room or at home for allergic bronchospasm, blood dyscrasias or convulsions that do not result in hospitalization, or development of drug dependency or drug abuse.

Is associated with liver injury and impaired liver function defined as:

- ALT \geq 3xULN and total bilirubin* \geq 2xULN (>35% direct), **or**
- ALT \geq 3xULN and INR** $>$ 1.5.

* Serum bilirubin fractionation should be performed if testing is available; if unavailable, measure urinary bilirubin via dipstick. If fractionation is unavailable and ALT \geq 3xULN and total bilirubin \geq 2xULN, then the event is still to be reported as an SAE.

** INR testing not required per protocol and the threshold value does not apply to participants receiving anticoagulants. If INR measurement is obtained, the value is to be recorded on the SAE form.

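### Table 5 (Section 8.3.4) asks for an SAE form on any isolated ALT ≥3×ULN, which contradicts the SAE definition in Section 10.2.2, Table 3 footnote 2 and other rows of Table 5

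*Protocol*

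**What the plan says.** Four places in the protocol bear on when a liver enzyme elevation is reported as an SAE.

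- **Section 8.3.4, Table 5, combined liver row.** The trigger is ALT ≥3×ULN with bilirubin ≥2×ULN, then "ULN (>35% direct) (or ALT" ≥3×ULN. The forms, due in 24 hours, are the "SAE” data collection tool. “Liver Event eCRF” and “Liver Imaging” and/or “Liver Biopsy” eCRFs, if applicable".
- **Section 8.3.4, Table 5, the next rows.** ALT ≥5×ULN persisting at least 2 weeks, and ALT ≥8×ULN, need a Liver Event eCRF and, at follow-up, an "Updated Liver Event eCRF". No SAE form is listed. A last row, also with the Liver Event eCRF only, covers ALT ≥3×ULN (baseline below ULN) or a threefold rise from baseline, with hepatitis or hypersensitivity symptoms.
- **Section 10.2.2.** The liver criterion for an SAE begins "Is associated with liver injury and impaired liver function defined as". It has two limbs: ALT ≥3×ULN with total bilirubin ≥2×ULN (>35% direct), or ALT ≥3×ULN with INR >1.5. A note adds: "INR testing not required per protocol and the threshold value does not apply to participants receiving anticoagulants".
- **Section 7.1.2, Table 3 footnote 2.** ALT >3×ULN with bilirubin >2×ULN (>35% direct) "must be reported as an SAE (excluding studies of hepatic impairment or cirrhosis". Isolated ALT is not named. The footnote also mentions an INR threshold that Table 3 does not state.

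Section 9.4.2 lists "Incidence of SAEs" among the planned adverse event summaries.

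**The concern.** Table 5 is what a site consults to decide which form to send and how fast. Its second trigger is bare, so it sends isolated enzyme elevations into the 24-hour SAE stream although the protocol's own definition does not make them serious. A site that follows Table 5 files an SAE form, while a site that follows Section 10.2.2 does not. Both can claim compliance.

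Two things are at stake: the consistency of expedited reporting across sites, and the meaning of the SAE incidence summary, which could depend on the passage a site happened to read.

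**Working it through.** The protocol states no figure to reproduce, so the check sets the conditions side by side.

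**Notation.** A = ALT ≥3×ULN. B = bilirubin ≥2×ULN with >35% direct. I = INR >1.5.

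**Logic of each passage.**

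- Table 5, combined row: (A and B) or A. This reduces to A, so B has no effect.
- Section 10.2.2: (A and B) or (A and I), which is A and (B or I). This is a subset of A.
- Table 3 footnote 2: A and B only, with strict inequalities (>3 and >2) where Section 10.2.2 uses ≥.

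**Difference.** The excess of Table 5 over Section 10.2.2 is every event with A true, B false, and I false or not measured, unless the event is serious for another reason. Since Section 10.2.2 is a subset of Table 5's trigger, the difference has one sign: Table 5 can add SAE forms but never remove them. Section 1.3 schedules INR only at Screening and Day 1, so on treatment I will usually be unmeasured.

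**Three example records**, each with normal bilirubin, no INR, no symptoms and no other seriousness criterion:

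| Record (baseline ALT below ULN) | Table 5 combined row | Other Table 5 rows | Section 10.2.2 | Table 3 footnote 2 |
|---|---|---|---|---|
| ALT 3.4×ULN, once | SAE form | None, or Liver Event eCRF (see below) | Not an SAE | Not named |
| ALT 5.5×ULN for 2 weeks | SAE form | Liver Event eCRF only | Not an SAE | Not named |
| ALT 8.5×ULN | SAE form | Liver Event eCRF only | Not an SAE | Not named |

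In the second and third records Table 5 contradicts itself: the rows written for larger elevations ask for less than the row that already catches them at 3×ULN.

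The first record depends on the last Table 5 row. If the symptom condition governs both halves of that row, an asymptomatic 3.4×ULN matches no row except the combined one. If it governs only the threefold-rise half, the record matches a Liver Event eCRF row and conflicts with the combined row in the same way as the other two.

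**Is the missing condition an extraction loss?** The bracket is closed, no redaction is marked and the rest of the row is intact. The likeliest explanation is a dropped INR condition, because the two limbs parallel Section 10.2.2 and footnote 2 keeps INR wording with no threshold to attach to. That remains an inference.

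**Consistency elsewhere.** Section 8.3.10.2, on Grade 1 or 2 events, handles ALT ≥3×ULN by consulting the Medical Monitor and mentions no SAE report. Section 7.1.2.1 asks for the SAE eCRF only where it applies, even when stopping criteria are met.

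**The case against.** The strongest reply is that Table 5 governs forms, not seriousness. Section 8.3 sends the reader to Section 10.2 for the definitions, and the lead-in to Table 5 ties reporting to the investigator finding that the event meets its protocol definition. Section 10.2.1 makes a laboratory value an AE only if judged clinically significant, and Section 10.2.2 says that what is not an AE cannot be an SAE. A Table 5 footnote also has the sponsor contacted at the onset of liver chemistry elevations, so misfiled reports could be caught.

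This stands in part. A reader might infer that Table 5 makes an isolated ALT ≥3×ULN an SAE. It does not; it asks for the SAE form. But the same lead-in separately names liver abnormalities meeting pre-defined criteria, and Table 5 prints such a criterion beside the form. A site that obeys the row is not misreading it.

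Three further inferences are not supported:

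- **That Section 7.1.1 contradicts Table 5** because a participant with ALT of 5 to <8×ULN (baseline ≤1.5×ULN) stays on treatment ("Participant can continue study intervention"). Continuing treatment and seriousness are separate questions, so that passage settles nothing here.
- **That SAE incidence is inflated by a stated percentage.** The protocol gives neither an expected rate of ALT ≥3×ULN nor an expected SAE incidence, and any percentage would also assume that every site follows Table 5 and that no report is corrected.
- **That the comparison is biased against one arm.** The table applies to both arms. Section 2.3.1 notes ALT-predominant elevations with cabotegravir, which makes such events foreseeable, but no imbalance is shown.

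**Conclusion.** Wrong as written: a document inconsistency in safety reporting. The combined liver row of Table 5 cannot be reconciled with Section 10.2.2, Table 3 footnote 2 or Table 5's own higher-ALT rows.

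The direction is certain. Relative to Section 10.2.2 the row can only add SAE reports, at most one for each isolated ALT event that a site reports under it. The number cannot be computed from the protocol. It depends on how often isolated ALT ≥3×ULN occurs, how many sites apply the row literally, and how many reports the sponsor later reclassifies. The primary endpoint, HIV-1 RNA ≥50 c/mL, is unaffected.

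The conclusion rests on reading the printed row as complete. It does not depend on the inference that INR is the dropped condition.

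**What to change.** 1. Reconcile the combined liver row of Table 5 with Section 10.2.2 and Table 3 footnote 2 so that all three state the same SAE trigger. In the same pass, align the inequalities (≥ or >) and settle the INR wording in footnote 2 that refers to a threshold Table 3 does not give.
2. State which Table 5 row, if any, covers an asymptomatic isolated ALT of 3 to <5×ULN, and whether the symptom condition in the last liver row governs both of its halves. Without this, correcting the combined row may leave such a record in no row.
3. Re-check any SAE already filed on isolated ALT against Section 10.2.2 before SAE incidence is summarised.

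The cost is an edit to one table row, a footnote and a clarifying line, by amendment or site memo, plus a short review of liver-related SAE reports. Only the reporting classification is at issue; nothing here asks for a change to a stopping or dosing rule.
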